4.1 Description

N-acetyl cysteine (or saline) IV infusion given as a 150 mg/kg loading dose over the first hour and then follow that with a 50 mg/kg maintenance dose infused over the next 4 hours

4.2 Treatment Regimen

A 150 mg/kg loading dose of NAC or saline over the first hour followed by a 50 mg/kg maintenance dose infused over the next 4 hours on days one of both parts of the study.

4.3 Method for Assigning Subjects to Treatment Groups

The investigational pharmacy at the University of Minnesota will be responsible for implementing the randomization order in which participants are given NAC or saline, prepared by the study statistician. This information will be blinded to investigators and participants and they will be unblinded only at the end of the study.

4.4 Subject Compliance Monitoring

Treatment will be witnessed by the investigators, so compliance will be assumed.

4.5 Prior and Concomitant Therapy

No restrictions

4.6 Packaging

- See Section 5.1

4.7 Blinding of Study Drug

The investigational pharmacy at the University of Minnesota Medical Center will prepare and dispense NAC or saline in blinded fashion. The solutions will be prepared to look the same so blinding is maintained. Half normal saline (0.45% NaCl) will be used as the diluent in the solution. Only the investigational pharmacy will have record of the drug assignment link to participant IDs.

4.8 Receiving, Storage, Dispensing and Return

4.8.1 Receipt of Drug Supplies

Upon receipt of the study treatment supplies, an inventory will be performed and a drug receipt log filled out and signed by the person accepting the shipment. The designated study staff will count and verify that the shipment contains all the items noted in the shipment inventory. Any damaged or unusable study drug in a given shipment (active drug or comparator) will be documented in the study files.

CONFIDENTIAL

4.8.2 Storage

See section 5.91

4.8.3 Dispensing of Study Drug

The investigational pharmacy at the University of Minnesota Medical Center will dispense the study drug or saline and will follow standard pharmaceutical protocols to reconcile the stock.

4.8.4 Return or Destruction of Study Drug

At the completion of the study, there will be a final reconciliation of drug shipped, drug consumed, and drug remaining. This reconciliation will be logged on the drug reconciliation form, signed and dated. Any discrepancies noted will be investigated, resolved, and documented prior to return or destruction of unused study drug. Drug destroyed on site will be documented in the study files.

5 Study Procedures

This study will consist of a screening visit and two 3-day intervention visits separated by approximately 8 weeks.

At the screening visit (approximately 2-4 days prior to study day one) informed consent will be obtained, the clinical history will be reviewed to be certain a volunteer meets the inclusion criteria and baseline hemoglobin A1c will be obtained.

Subjects will be asked to report to the research center by 7 am on the first day of the study after fasting overnight. On arrival, intravenous lines will be placed in each arm (one will be used for infusions and the other for blood sampling). A minimum of 30 minutes after the IVs are placed, baseline blood samples will be drawn for glucose, epinephrine, norepinephrine, cortisol, cysteine and glutathione measurements. Subjects will then be given diphenhydramine 25 mg IV push immediately prior to the start of a 60 minute infusion of NAC (150 mg) or a similar volume of saline between 8 am and 9 am, followed by a four hour infusion of 50 mg of NAC. Thirty minutes after the start of the NAC infusion, a hyperinsulinemic (2.0 $\mu\text{u/kg/min}$) hypoglycemic (target = 50 mg/dl) clamp protocol will be started. During the morning study, blood samples will be collected every 5 minutes for monitoring of blood glucose levels and every 15 minutes for later measurement of serum epinephrine, norepinephrine, cortisol. Plasma and red blood cells samples will also be collected every 15 minutes for later measurement of NAC, cysteine, glutathione, and GSH/GSSG ratios (redox status). During the final 15 minutes of the morning clamp, subjects will be asked to quantitate their symptoms using a standardized method (13). At the completion of the morning clamp, glucose will be given to return the participant to euglycemia. 2 hours after the end of the morning clamp, a second hyperinsulinemic (2.0 $\mu\text{u/kg/min}$) hypoglycemic (target = 50 mg/dl) clamp protocol will be followed over two hours. The afternoon clamp study will proceed as in the morning except that no serum or plasma will be collected except for the monitoring of glucose and collection of samples for subsequent measurement of NAC,

CONFIDENTIAL

cysteine, glutathione, and GSH/GSSG ratios. After the completion of the afternoon clamps, subjects will be returned to euglycemia and fed a meal. They will then be allowed to leave the research center with instructions to return the next morning. At 7 AM on day 2 they will undergo a single 2 hour hyperinsulinemic hypoglycemic stepped clamp (75, 65, 55, 45 mg/dl targets) during which blood samples will be collected as on the morning of day 1. Symptom scores will be collected in the final 15 minutes of each step in the clamp. At the end of the study, infusions will be stopped, they will be fed and meal and then be sent home after they are scheduled to return for Part 2 in 8 weeks. This timing is selected to ensure that female participants are studied at the same phase of the menstrual cycle; males will return for Part 2 in 8±2 weeks. During Part 2 they will receive the treatment not provided during Part 1 in a blinded fashion. The rest of the study protocol will be the same as in Part 1.

A description of the study visits is below:

Visit description	Expected activities
Screening	
 • Confirm subject qualification • Obtain informed consent • Baseline A1c
Part 1 Day 1	
 • Randomization • Morning (8 – 10 AM) hyperinsulinemic hypoglycemic clamp study with infusion of NAC or saline depending on randomization assignment, collection of counterregulatory hormones and hypoglycemia symptom scores • Afternoon (1 – 3 PM) hyperinsulinemic hypoglycemic clamp study with infusion of NAC or saline depending on randomization assignment
Part 1 Day 2	
 • Hyperinsulinemic stepped hypoglycemic clamp study with collection of counterregulatory hormones and hypoglycemia symptom scores • Lunch
8 week wash out period	Usual activities
Part 2 Day 1	
 • Morning (8 – 10 AM) hyperinsulinemic hypoglycemic clamp study with infusion of NAC or saline depending on randomization assignment, collection of counterregulatory hormones and hypoglycemia symptom scores • Afternoon (1 – 3 PM) hyperinsulinemic hypoglycemic clamp study with infusion of NAC or saline depending on randomization assignment
Part 2 Day 2	Hyperinsulinemic hypoglycemic clamp study with collection of counterregulatory hormones and hypoglycemia symptom scores 
 • Lunch

CONFIDENTIAL

6 Statistical Plan

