Diagnosis and Main Inclusion Criteria	Healthy adults ages 18-65 years with hemoglobin A1c < 6.0%. Exclusion criteria will include history of diabetes, hyperglycemia, stroke, seizures, arrhythmias, active cardiac disease; pregnancy or plan to become pregnant during the study period; diagnosis of asthma; use of anti-oxidants or drugs that can alter glucose metabolism; and concomitant medical problems that may prevent the subject from successfully completing the protocol.
Study Product, Dose, Route, Regimen	N-acetyl cysteine 200 mg/kg (or saline) IV infusion (given as a 150 mg/kg loading dose over the first hour and then followed by a 50 mg/kg maintenance dose infused over the next 4 hours on day 1 of each of the two parts of the study)
Duration of administration	5 hours on day one

Reference therapy	NAC will be tested against placebo.
Statistical Methodology	
Our primary outcome is the peak epinephrine response during the third hypoglycemic clamp of each infusion experiment, thus each participant will have two observations: one from their NAC infusion experiment and one from their saline infusion experiment. We will fit a general linear mixed model with fixed effects for treatment (NAC vs. saline), treatment order (NAC first vs. saline first), and period (Part 1 vs. Part 2) and a random effect for participant. We will also consider adjustment for important baseline characteristics, such as age, gender, and duration of diabetes. Diagnostics will be examined to assess model assumptions. Secondary outcomes include: the within-person difference in peak epinephrine response between the first hypoglycemic clamp (when an infusion is given) and the third hypoglycemic clamp (when no infusion is given) of each infusion experiment; symptom scores during the third hypoglycemic clamp of each infusion experiment; and the within-person difference in symptom scores between the first hypoglycemic clamp and the third hypoglycemic clamp of each infusion experiment

CONFIDENTIAL

1 Introduction

This document is a protocol for a human research study. This study will be conducted according to US and international standards of Good Clinical Practice (FDA Title 21 part 312 or 812 and International Conference on Harmonisation guidelines), applicable government regulations and Institutional research policies and procedures.

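### Section 5 offers saline only for the first hour of the study infusion and then names NAC alone for the next four hours, in conflict with the sections that describe a saline control throughout

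*Combined protocol and SAP*

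**What the plan says.** The Section 5 narrative, which sets out the day 1 procedure step by step, names NAC for a 60-minute phase, with this alternative and continuation: "a similar volume of saline between 8 am and 9 am, followed by a four hour infusion of 50 mg of NAC". No saline alternative is written for the four-hour phase.

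Section 4.2 reads "A 150 mg/kg loading dose of NAC or saline over the first hour followed by a 50 mg/kg maintenance dose infused over the next 4" (the unit being hours). Here the words allowing saline sit with the loading dose, and the maintenance agent is not named.

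Other current text treats saline as the alternative to the whole infusion:

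- The study product row of the Study Summary has "N-acetyl cysteine 200 mg/kg (or saline) IV infusion" and then lists both phases. The next rows give the duration as "5 hours on day one" and name placebo as the reference.
- Sections 1.2 and 4.1 put saline in parentheses ahead of both phases.
- The visit table in Section 5 describes the second session as "Afternoon (1 – 3 PM) hyperinsulinemic hypoglycemic clamp study with infusion of NAC or saline depending on randomization assignment", with matching text for the morning. The paragraph above the table says that Part 2 delivers whichever treatment was not given in Part 1.
- Sections 6.1 and 6.2 rest on one NAC experiment and one saline experiment per person.

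**The concern.** The primary analysis compares the epinephrine response on day 2 after a NAC infusion with the response after a saline infusion in the same person. Its meaning depends on the control containing no NAC. Section 5 is the text that staff would follow on the day, and on its face it runs NAC in hours 2 to 5 whatever the assignment.

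Two things would be at stake if that text were carried into a preparation order:

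- **The contrast.** It would become the full regimen against the maintenance phase alone, not NAC against none. If the maintenance phase acts in the same direction as the full regimen, the difference shrinks toward zero.
- **The safety count.** Section 7.5 has the monitoring board record a reaction during a saline infusion as a placebo reaction and exclude it from the cumulative number compared with the stopping boundary. That would be a misclassification if NAC was running. Section 2.4 schedules allergy checks at 30, 60 and 90 minutes after the infusion starts, and the 90-minute check falls inside the four-hour phase.

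Section 4.7 requires the solutions to look the same, so the blinded team could not see such an error. The NAC assays described in Section 5 could reveal it later, but could not restore the contrast in a crossover planned around 15 completers.

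**Working it through.** **Plan's own figures.** Duration: 1 h + 4 h = 5 h, which agrees with the Study Summary. Amount: 150 + 50 = 200 mg/kg, which also agrees.

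**What the control receives, by source.**

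| Source | First hour | Next four hours |
|---|---|---|
| Study Summary; Sections 1.2 and 4.1 | saline | saline |
| Section 4.2 | saline | agent not named |
| Section 5, narrative, read literally | saline | NAC |
| Section 5, visit table and crossover rule | saline or NAC by assignment | saline or NAC by assignment |
| Sections 6.1 and 6.2 | saline experiment | saline experiment |

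**Size of the literal reading.** Share of infusion time with NAC in the control: 4/5 = 80%. Share of the active condition's amount: 50/(150 + 50) = 25%. The 25% does not depend on whether the figures are mg, as in Section 5, or mg/kg, as elsewhere; that difference is a separate matter. Under the other sources both shares are 0%.

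**Overlap with the day 1 clamps under the literal reading.** The four-hour phase covers minutes 60 to 300 from the start of the infusion. The overlap depends on which of the protocol's two timelines is used.

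- *Section 5 narrative:* clamp 1 starts at minute 30 and lasts two hours (30 to 150). Clamp 2 starts two hours after clamp 1 ends and lasts two hours (270 to 390). Overlap with clamp 1: 150 − 60 = 90 of 120 minutes. Overlap with clamp 2: 300 − 270 = 30 of 120 minutes.
- *Visit-table clock times, assuming the infusion starts at 8 AM:* clamp 1 is 8 to 10 AM (0 to 120) and clamp 2 is 1 to 3 PM (300 to 420). Overlap with clamp 1: 120 − 60 = 60 minutes. Overlap with clamp 2: 0 minutes.

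**Effect on the primary contrast.** The documents give no dose-response for NAC on the epinephrine response, and no information on whether the loading phase or the maintenance phase matters more. The 25% share therefore cannot be turned into a loss of effect or of power.

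**The case against.** The strongest defence is that Section 5 does not mean what its one sentence says, and most of that defence stands.

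- The next sentence starts the clamp 30 minutes after the start of what it calls the NAC infusion. Both conditions are clamped, so the term there must be shorthand for the blinded study infusion. Taken literally, a saline session would have no NAC until minute 60 and would not be clamped until minute 60 + 30 = 90.
- The visit table in the same section restores the saline alternative, and the crossover rule presupposes two distinct treatments. One clause stands against nearly everything else in the protocol.
- In Section 4.2 the saline alternative can naturally carry forward into the maintenance phase. That section is ambiguous; it is not a second instance of NAC-only maintenance.

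A milder reading attaches the four-hour clause to the NAC option alone. That removes the contradiction about the agent, but the narrative then does not say what the control receives in hours 2 to 5. The text needs correcting on either reading.

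A reader might also infer a conflict about the vehicle, because Section 4.7 specifies that "Half normal saline (0.45% NaCl) will be used as the diluent in the solution" while other sections say only saline, or because saline appears beside mg/kg figures. The documents do not support this. Half normal saline is a kind of saline, and the parenthetical in Sections 1.2 and 4.1 need not be a weight-based saline dose.

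**Conclusion.** The concern holds as an inconsistency in an operative instruction. The Section 5 narrative omits the saline alternative for the four-hour phase, Section 4.2 is ambiguous about that phase, and the other sections cited describe a control that is saline or placebo for the whole infusion. It is most likely a drafting omission, but it should be corrected because it sits in the procedure itself.

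Followed literally, it would place NAC in 4 of 5 control hours, at 25% of the active amount. It would overlap the two day 1 clamps by 90 and 30 minutes, or by 60 and 0 minutes, depending on the timeline used. If saline throughout is what is intended and prepared, there is no effect on the trial beyond the text.

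Two stronger conclusions are tempting and not supported. One is that control participants will receive, or have received, NAC: the weight of the protocol points the other way, and the pharmacy order is not in the documents. The other is that a particular loss of power follows: any such figure would need an assumed dose-response. What can be said is that the bias would run toward no difference, provided the maintenance phase acts in the same direction as the full regimen, and that the stopping count under Section 7.5 could be too low.

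**What to change.** Reconcile the Study Summary, Sections 1.2, 4.1 and 4.2, and the narrative and visit table of Section 5, so that they state consistently what the saline condition receives in the 60-minute phase and in the four-hour phase. The sponsor decides the intended wording. Confirm that the investigational pharmacy's preparation order agrees with the reconciled text.

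The cost is a wording amendment, submitted to the IRB as Section 10 requires, and one check of the pharmacy order. No additional participants, procedures or staff are needed, and the statistical model does not change.

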12 PUBLICATION PLAN19

13 REFERENCES20

14 ATTACHMENTS20

List of Abbreviations

List all abbreviations used in protocol

AE	Adverse Event
CFR	Code of Federal Regulations
CRF	Case Report Form
DSMB	Data and Safety Monitoring Board
DSMP	Data and Safety Monitoring Plan
FDA	Food and Drug Administration
GCP	Good Clinical Practice
HIPAA	Health Insurance Portability and Accountability Act of 1996
ICH	International Conference on Harmonisation
IDS	Investigational Drug Services
IRB	Institutional Review Board
PHI	Protected Health Information
SAE	Serious Adverse Event

CONFIDENTIAL

This material is the property of the University of Minnesota. Do not disclose or use except as authorized in writing by the study sponsor

Study Summary

Title	A randomized double blinded study to examine the use of N-acetyl cysteine for the prevention and treatment of HAAF in patients with type 1 diabetes
Short Title	NAC for HAAF
Protocol Number	NA
Phase	I/II
Methodology	This is a single center, double blind randomized cross over design trial that will compare the impact of N-acetyl cysteine (200 mg/kg) vs. saline infusion during experimental hypoglycemia on day one on the responses to experimental hypoglycemia on day two. 18 participants will be studied twice, 8 weeks apart. On each occasion they will undergo a 2 hour hypoglycemic clamp (target 50 mg/dl) in the morning and in the afternoon on day one and then again on the morning of day 2. During the morning clamps, samples will be collected for later measurement of serum epinephrine levels, plasma and red blood cell NAC, cysteine, and glutathione concentrations and GSH/GSSG ratios (redox status), and participants will be asked to complete a hypoglycemia symptom questionnaire
Study Duration	10-12 weeks per subject
Study Center(s)	Single Center
Objectives	Primary endpoint will be the within person difference in epinephrine secretion during the morning episodes of hypoglycemia on days one and two under the two treatment conditions. Epinephrine secretion during hypoglycemia is assessed by collecting blood samples for measurement of epinephrine concentrations at baseline and every 15 minutes during the period of hypoglycemia (starting at point where blood glucose is first \leq 55 mg/dl) in the clamp studies done in the mornings of days 1, 2, and 3 of both parts 1 and 2.
Number of Subjects	36

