6.3 Subject Population(s) for Analysis

In this version of the protocol, we intend to only study healthy volunteers. In the original version, we intended to enroll humans with type 1 diabetes of less than 20 years duration, with A1c 6.9-8.2%, who were aware of hypoglycemia but were unable to reach our recruitment goals with this population. More than 45 potential participants were contacted over 14 months and only one subject was able to complete the entire protocol. The reasons potential participants refused enrollment included strong preferences to not experience hypoglycemia and inability to commit the time necessary to complete the study. Previously our group has had no trouble enrolling enough normal volunteers to participate in studies in which they were asked to experience several periods of hypoglycemia. Thus, we believe that we will meet our recruitment goals by changing the population to normal volunteers. In addition, this is a proof of principle study in which the impact of NAC on hypoglycemia induced blunting of the counterregulatory response will be measured. Normal volunteers who participate in this protocol are expected to have the same degree of hypoglycemia induced blunting in their counterregulatory response as patients with type 1 diabetes and normal awareness of hypoglycemia. Therefore, this redesign will allow us to determine if NAC works under controlled conditions. If it does, it will provide rationale to use in in patient populations in the future.

Exclusion criteria will include history of diabetes, hyperglycemia, stroke, seizures, arrhythmias, active cardiac disease, pregnancy or plan to become pregnant during the study period; diagnosis of asthma (increases risk of hypersensitivity reactions to NAC); use of anti-oxidants or drugs that can alter glucose metabolism; concomitant medical problems that may prevent the subject from successfully completing the protocol; and an unwillingness to avoid exercise during the 7 days before each part of the study.

7 Safety and Adverse Events

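### Section 5 prints the day 1 clamp insulin rate in micro-units, about 0.017 units over two hours at 70 kg, which does not fit a hyperinsulinemic clamp to 50 mg/dl

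*Combined protocol and SAP*

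**What the plan says.** The insulin rate appears only in Section 5 (Study Procedures), once for each day 1 clamp.

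- Morning clamp: "a hyperinsulinemic (2.0 $\mu\text{u/kg/min}$) hypoglycemic (target = 50 mg/dl) clamp protocol will be started".
- Afternoon clamp: "a second hyperinsulinemic (2.0 $\mu\text{u/kg/min}$) hypoglycemic (target = 50 mg/dl) clamp protocol will be followed over two hours".

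The Methodology row of the Study Summary gives the duration of both: "they will undergo a 2 hour hypoglycemic clamp (target 50 mg/dl) in the morning and in the afternoon on day one".

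For day 2, Section 5 says "they will undergo a single 2 hour hyperinsulinemic hypoglycemic stepped clamp (75, 65, 55, 45 mg/dl targets". It labels that clamp hyperinsulinemic too but states no rate.

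The documents contain no priming dose, total insulin dose or target insulin level. Section 4 (Study Drug) covers only NAC and saline. On who is studied, Section 6.3 says: "In this version of the protocol, we intend to only study healthy volunteers".

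**The concern.** A rate in micro-units per kg per minute delivers hundredths of a unit over two hours. That is hard to square with a clamp described as hyperinsulinemic and meant to bring a person without diabetes down to 50 mg/dl. The label, the target and the rate stand in the same sentence, so the inconsistency is internal to Section 5.

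Two things make it worth correcting. Insulin is a high-risk drug, given here to healthy volunteers, and this is the only written instruction for it. The day 1 clamps are also the exposure meant to blunt the epinephrine response at the third clamp, which Section 6 names as the primary outcome. If staff use a rate other than the printed one, the protocol does not record what it was.

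**Working it through.** The plan states no total insulin amount or insulin concentration, so there is no figure of its own to reproduce. The check is whether the printed rate is compatible with the label and target beside it.

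**Inputs from the documents**
- Rate: 2.0 micro-units/kg/min (Section 5, both day 1 clamps).
- Duration: 2 hours, or 120 minutes (Study Summary; Section 5 for the afternoon clamp).
- Glucose target: 50 mg/dl (Section 5).

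**Assumptions not in the documents**
- Body weight: 70 kg, range 50 to 120 kg.
- Insulin runs at the printed rate for the full 120 minutes.
- Insulin clearance: 5 to 30 ml/kg/min.
- Fasting insulin: 3 to 10 micro-units/ml.
- For the extreme bound in step 4 only, distribution volume: 40 to 150 ml/kg.

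**Step 1. Total insulin per clamp** = rate × weight × minutes ÷ 1,000,000.

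| Weight (kg) | Calculation | Micro-units | Units |
|---|---|---|---|
| 50 | 2.0 × 50 × 120 | 12,000 | 0.012 |
| 70 | 2.0 × 70 × 120 | 16,800 | 0.0168 |
| 100 | 2.0 × 100 × 120 | 24,000 | 0.024 |
| 120 | 2.0 × 120 × 120 | 28,800 | 0.0288 |

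**Step 2. Steady-state rise in plasma insulin** = rate ÷ clearance; weight cancels.
- Clearance 5 ml/kg/min: 2.0 ÷ 5 = 0.4 micro-units/ml.
- Clearance 30 ml/kg/min: 2.0 ÷ 30 = 0.067 micro-units/ml.

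**Step 3. Rise relative to fasting insulin.**
- Largest: 0.4 ÷ 3 = 13%.
- Smallest: 0.067 ÷ 10 = 0.7%, or about 1%.

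**Step 4. Extreme bound with no clearance at all** = rate × minutes ÷ volume.
- 2.0 × 120 ÷ 40 = 6 micro-units/ml.
- 2.0 × 120 ÷ 150 = 1.6 micro-units/ml.

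This bound supposes that no infused insulin is removed in two hours and is reached only at the end of the clamp. Even so, the rise is no larger than the order of the assumed fasting level itself.

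**Step 5. Search for a correcting figure.** The Study Summary, Sections 1 to 4, the visit table in Section 5, and Sections 6 and 7 give no insulin rate. Nothing elsewhere overrides or explains the printed unit.

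**The case against.** **The micro sign may come from the PDF reading.** It sits in markup made by the conversion program, and that program handles symbols unevenly: the less-than-or-equal sign before 55 mg/dl is coded differently in the Study Summary and in Section 2.2. The two occurrences are the same string in one paragraph, so a systematic misread would repeat and the second does not confirm the first independently. This stands. The sign must be checked in the source PDF before the point is sent.

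**No second figure in the documents contradicts the rate.** Hyperinsulinemic is not defined numerically, so the argument needs clearance and fasting values from outside. This stands as a limit on the kind of evidence. It does not remove the inconsistency, because the result is the same across wide ranges of weight, clearance and fasting insulin.

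**A reader might infer that the trial would produce no hypoglycemia, or that operators would choose different rates and add noise to the NAC versus saline comparison.** The documents do not support either inference. The exposure is defined by glucose targets, with glucose sampled every 5 minutes, so failure to reach target would be seen at once. The study is single-center, Section 6.1 reports an earlier clamp study by the same group, and Section 6.3 describes their experience with repeated hypoglycemia in normal volunteers. Nothing shows rates varying between operators.

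**A reader might also infer that the missing day 2 rate leaves the primary outcome uncontrolled between parts.** Section 5 already says that, apart from the switch of treatment, Part 2 follows Part 1. The missing day 2 rate is absent detail. It does not depend on the micro sign and does not strengthen the unit point.

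**Experienced staff would recognize a unit slip.** Probably so, but then the working rate comes from outside the protocol, and the written figure still needs correcting.

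**Conclusion.** The point holds as a unit inconsistency in Section 5, provided the micro sign is in the source PDF. As printed, the only insulin rate in the documents amounts to about 0.017 units per two-hour clamp at 70 kg, and 0.012 to 0.029 units over 50 to 120 kg. On the stated assumptions it raises insulin by about 1 to 13% above fasting. That is a small rise rather than none, but not a material one, and it does not fit a hyperinsulinemic clamp with a 50 mg/dl target.

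The severity is that of a simple correction to a safety-relevant figure. No bias, added variance or loss of power has been shown, and sample size, power and alpha are unaffected. The point is separate from how Section 5 writes the NAC dose.

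**What to change.** 1. Confirm the micro sign in the source PDF at both places in Section 5. If it is not there, the unit point falls away.
2. If it is there, the sponsor should reconcile the printed rate and unit with the clamp order actually used, and with the label and glucose target beside it, and amend both day 1 sentences together. No rate is proposed here; the sponsor must supply it.
3. As a secondary clarification, the sponsor could record the insulin rate for the day 2 clamp in the same amendment. The existing statement that Part 2 follows Part 1 would then carry it forward.

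The cost is a short wording amendment to Section 5, with no change to visits, staffing, sample size or analysis.

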2.1 General Design

This is a single center, double blind randomized cross over design trial that will compare the impact of NAC vs. saline infusion during experimental hypoglycemia on day one on the responses to experimental hypoglycemia on day two. Figure 1 shows the protocol in schematic form. We intend to enroll 18 individuals to obtain the complete data sets from 15 participants.

Expected duration of subject participation is 10-12 weeks. This study will consist of a screening visit and two 2-day intervention visits separated by approximately 8 weeks.

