3.1 Inclusion Criteria

- Healthy volunteer
- Age 18 – 65 years
- Hemoglobin A1c < 6.0%

CONFIDENTIAL

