3.3 Subject Recruitment and Screening

Subjects will be recruited from a registry of normal volunteers who are interested in participating in research that is maintained by the investigator. In addition, subjects will be drawn from the community using IRB approved public notices. The only laboratory testing necessary to meet inclusion/exclusion criteria will be a hemoglobin A1c done in the last month.

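### An 8-week gap keeps women in the same menstrual phase only if their cycle is near 28 days, and the protocol collects no cycle information

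*Combined protocol and SAP*

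**What the plan says.** Section 5 (Study Procedures) has participants "scheduled to return for Part 2 in 8 weeks" and gives the reason: "This timing is selected to ensure that female participants are studied at the same phase of the menstrual cycle". The same sentence gives men a window: "males will return for Part 2 in 8±2 weeks". No window is given there for women.

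Two other places describe the interval more loosely and for both sexes. Section 2.1 has "two 2-day intervention visits separated by approximately 8 weeks", and the opening of Section 5 has "two 3-day intervention visits separated by approximately 8 weeks". (These two also disagree on whether a visit lasts two days or three, which is a separate matter.) Section 6.2 states the washout as 8 weeks, without a range.

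On who is enrolled and what is collected:

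- Section 3.1 admits "Age 18 – 65 years". Sections 3.1 and 3.2 set no criterion on cycle length, regularity or menopausal status.
- Section 3.3 states: "The only laboratory testing necessary to meet inclusion/exclusion criteria will be a hemoglobin A1c done in the last month".
- Section 4.5 on other therapy reads "No restrictions". Section 3.2 excludes drugs that affect glucose metabolism, but hormonal contraception is not mentioned.
- The visit table in Section 5 has no entry for last menstrual period or cycle day.
- The model in Section 6.2 has terms for treatment, order, period and participant, and none for phase.

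**The concern.** The protocol names a property it wants, the same menstrual phase in both parts, and relies on a calendar interval to secure it. A calendar interval can do that only for women whose cycle divides it, or nearly does. The documents describe nothing else that would secure the match or show afterwards whether it was achieved.

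The treatment effect is estimated from differences within about 15 people. If phase affects the epinephrine response, a woman studied in different phases contributes a NAC–saline difference that also contains a phase difference. The protocol does not state that phase affects epinephrine. It treats phase only as something worth holding constant.

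**Working it through.** **Inputs.** The interval is 8 × 7 = 56 days (Section 5). The men's window is 8±2 weeks, or 42 to 70 days (Section 5). The detectable difference is 154 units with 15 completers, one-sided 5% error and 85% power, and the SDs from the earlier study are 168 and 134 pg/ml (Section 6.1). Cycle length L is not in the documents, so it is assumed and shown as a range.

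**Step 1: the plan's own figure.** Section 6.1 gives no SD for the within-person difference. Assuming zero within-person correlation:

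- SD of difference = √(168² + 134²) = √46,180 = 214.9.
- Normal approximation: (1.645 + 1.036) × 214.9 / √15 = 148.8.
- Noncentral t, 14 df: 156.6.
- Power at 154: 84.0% (t) or 87.1% (normal), against 85% stated.

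The 154 is therefore approximately reproduced without any gain from within-person correlation. It takes no explicit credit for phase matching. Exactly 154 at 85% power (t, 14 df) needs an SD of the difference of 211.4.

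**Step 2: phase shift at 56 days.** The shift is the signed distance of 56 from the nearest multiple of L. For L from 23 to 37 days the nearest multiple is 2L, so the shift is 56 − 2L = 2 × (28 − L).

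| Assumed L (days) | Shift (days) | Share of cycle |
|---|---|---|
| 24 | +8 | 33% |
| 26 | +4 | 15% |
| 27 | +2 | 7% |
| 28 | 0 | 0% |
| 29 | −2 | 7% |
| 30 | −4 | 13% |
| 32 | −8 | 25% |
| 35 | −14 | 40% |

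Between 21 and 40 days, 56 is a whole multiple of L only at L = 28. If the 8 weeks are counted from Part 1 Day 2, the gap from Day 1 to Day 1 is 57 days and each signed shift moves by +1 day.

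**Step 3: bias or noise?** Order is randomised, so a phase shift from Part 1 to Part 2 is not linked to which treatment comes second. Any average shift falls on the period term, and variation between women remains as noise. The gender adjustment that Section 6.2 may consider cannot remove a change within one woman between parts.

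**Step 4: illustration of size.** The extra SDs x below are assumptions, not values from the documents. If a fraction f of participants is affected, the SD of the difference becomes √(211.4² + f·x²), and power is taken at 154.

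| x (pg/ml) | Power, f = 0.5 | Power, f = 1 |
|---|---|---|
| 30 | 84.7% | 84.4% |
| 60 | 83.7% | 82.5% |
| 100 | 81.5% | 78.2% |

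**Step 5: would cycle-based dates fit the men's window?** Two cycles of 21 days last 42 days, and two of 35 days last 70 days. For an assumed range of 21 to 35 days, two own cycles fall within 6 to 10 weeks.

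**The case against.** The strongest reply is that the interval is not rigid. Sections 2.1 and 5 call it approximate, and because same-phase testing is the stated purpose, staff could move a woman's date to meet it. That stands in part: a reader might infer a strict 56-day rule, and the documents do not impose one. But they give no rule for using the latitude and do not ask for the information it would require.

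Second, the aim is the same phase, not the same cycle day. A 2-day shift, at 27 or 29 days, may well leave a woman in the same phase, and women without natural cycles are unaffected. This stands. It would be wrong to conclude that matching fails for every woman whose cycle is not exactly 28 days.

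Third, the wider window for men might be read as the wrong way round. It is not. Men have no phase to match, and an unconditional ±2 weeks for women would make matching worse. What is missing is a link between a woman's date and her cycle.

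Fourth, no loss is demonstrated. The number of women, their cycle lengths and the effect of phase on epinephrine are all unknown. This also stands and limits the weight of the point.

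**Conclusion.** The word *ensure* in Section 5 is not supported. An interval of 8 weeks aligns phase for cycles near 28 days. For assumed cycles further away, the shift grows by 2 days for each day of departure, reaching 8 days at 24 or 32 and 14 at 35. As the protocol is written, a mismatch could be neither avoided nor detected. The case report form is not among the documents, so this conclusion concerns the protocol text.

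The consequence is possible added noise in the within-person contrast. Its size cannot be computed from the documents. Under the assumed values above, with half of participants affected, power at 154 falls from 85% to between 84.7% and 81.5%.

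A reader might infer that the treatment comparison is biased or that the stated power depends on phase matching. The documents support neither: order is randomised, and 154 is approximately reproduced with zero within-person correlation. The point is minor.

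**What to change.** In Section 5:

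- For women with regular natural cycles, set Part 2 Day 1 to the same cycle day as Part 1 Day 1, two of their own cycles later, within the 8±2 weeks already used for men.
- For women without regular natural cycles, keep approximately 8 weeks.
- Record cycle day at both parts, usual cycle length, and contraceptive or menopausal status.
- Replace *ensure* with wording that matches what the rule can deliver.

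Then reconcile the four statements of the interval: 8 weeks, approximately 8 weeks and 8±2 weeks in Sections 2.1 and 5, and the 8-week washout in Section 6.2.

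The cost is a few sentences of protocol text and a short addition to the case report form. Scheduling becomes slightly less predictable, and women's washout would vary between 6 and 10 weeks, as it already may for men.
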